## 9.2 PROTOCOL DEVIATIONS AND VIOLATIONS

All major protocol deviations will be identified. A sensitivity analysis of the primary end point will be performed based on per-protocol analysis population. All the major protocol deviations will be listed. The decision regarding the major protocol deviations will be taken during the masked data review meeting. All the major protocol deviations will be identified and recorded in the Clinical Trial Management System (CTMS) of PRA.

## 9.3 DEMOGRAPHIC AND BASELINE CHARACTERISTICS

Demographic and baseline characteristics (gender, age, weight, height) will be summarized using descriptive statistics. Qualitative variables (gender) will be summarized using frequencies while quantitative variables (age, weight, height) will be summarized using mean, SD, median, Q1, Q3, minimum and maximum.

Demographic and baseline characteristics will be summarized for the ITT and Safety Population. The analysis will be presented in two ways: Best-GS010 vs Best-Sham and Worst-GS010 vs Worst-Sham.

---

This data will also be listed based on the data listed in the eCRF.

Medical history data will be summarized by using counts and percentages and will be presented by system organ class and preferred term. Duration of vision loss at the time of treatment will be summarized by treatment group (All-GS010 vs All Sham, Best-GS010 vs Best-Sham and Worst-GS010 vs Worst-Sham). For the All-GS010 versus All-Sham comparison the safety population will be used for analysis, whereas for the Best-GS010 versus Best-Sham comparison and the Worst-GS010 versus Worst-Sham comparison the ITT population will be used for analysis of the duration of vision loss.

## **9.4 TREATMENTS**

### **9.4.1 Extent of Study Drug Exposure**

This study includes a single IVT injection in randomized eye and a single sham IVT injection in fellow eye on same day. Therefore, no summary table will be produced for the exposure data. eCRF data related to IMP administration will be listed.

### **9.4.2 Concomitant Treatments**

Prior and concomitant treatments will be coded using the World Health Organization dictionary (WHO Drug Dictionary Version 01Mar2015 DDE, B2). For each medical entity all Anatomical Therapeutic-Chemical (ATC) codes will be assigned according the therapeutic classes to which the treatment belongs. Coding of Treatments is detailed in the Coding Guidelines.

Prior and concomitant treatments will be summarized for the Safety population by number and percentage of subjects of WHO Drug Dictionary ATC levels (ATC1, ATC2) and preferred term. All prior and concomitant treatment data will be listed.

## **9.5 EFFICACY ANALYSES**

All efficacy analysis will be conducted on the ITT population and analyzed by actual treatment received. Sensitivity analysis will be performed based on a PP Population.

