12.3 Analysis Populations

12.3.1 Intent-to-Treat Population

The intent-to-treat population will consist of all subjects, who are randomized and receive study treatment (GS010 or sham treatment). This population will be the population for the primary efficacy analysis.

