### 3.3 SAMPLE SIZE CONSIDERATIONS

Sample size calculation is based on the primary endpoint (LogMAR) and on the paired comparison of treated and sham eye. There is no published data regarding the within subject variance and the sample size calculation through paired comparison will therefore be very speculative for two reasons. The first reason is the within subject correlation between right and left eye and the second reason is the absence of information on the within and between subject variance of the LogMAR. Usually the within subject correlation is positive and the use of a null correlation is conservative. The absence of information on the LogMAR requires a second rough approximation of the mean and variance of LogMAR because the mean of ETDRS (Lam et al. 2014) is highly correlated to the variance of ETDRS ( $R^2 = 0.839$  for the log-log relationship). This correlation is in favor of the use of the LogMAR to stabilize the variance but the transformation from ETDRS mean and variance to LogMAR mean and variance requires additional assumptions. Starting with a mean 23.4 and a standard deviation of 28.3 (Lam et al.

2014) and a difference of 20 letters on average between treated and sham eye, using the relationship between the log mean and the log variance obtained with Lam et al. (2014) results (log variance = 1.743 log mean + 0.48,  $R^2 = 0.839$ ) and assuming a perfect lognormal distribution of ETDRS, the difference in means of the lognormal distributions is 0.65 (3.32 - 2.67) and the pooled standard deviation of the log distributions is 0.914. Assuming no correlation between both eyes, the within subject standard deviation is  $(2 \times 0.914^2)^{0.5} = 1.29$ . The standardized difference in means is therefore  $0.65/1.29 = 0.504$  rounded to 0.50. The sample size required to get a power of 85% is exactly 36 subjects.

In GS-LHON-CLIN-01(Phase I/II study), at week 48 the standard deviation (SD) for visual acuity of the between-eye difference in change from baseline was calculated as 0.594. Considering that in Phase III studies of GS010 detection of a 15 ETDRS letters or 0.3 LogMAR difference between treated and untreated eyes at outcome is a clinically reliable difference, the SD of the difference of 0.594 would provide a power/probability of 84% to detect such a difference based on the enrolment goal of 36 subjects each in the RESCUE and REVERSE Phase III clinical trials.

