### 3.4 RANDOMIZATION

The right eye of each subject will be randomly allocated to receive either GS010 or sham treatment in a 1:1 allocation ratio. The fellow (left) eye will receive the treatment not allocated to the right eye. Therefore, each subject will receive GS010 in one eye and sham treatment in the fellow eye. Prior to randomization, each subject's best- and worst-seeing eye will be determined. Efron's minimization method will be used in the randomization process to balance as much as possible the two treatment groups (GS010 and sham) in the best-seeing eyes.

To enroll a subject (Visit 1), the Investigator will call an interactive response system (IRS) and provide brief details about the subject to be enrolled. Each subject will receive a subject number assigned at screening, which will serve as the subject identifier throughout the study. The subject number will be required in all communication between the Investigator (or designee) and the IRS regarding a particular subject. Subject numbers will be tracked via the IRS.

To randomize a subject (Visit 2), the Pharmacist (or designee) will call the IRS and provide brief details about the subject to be randomized. Eligible subjects will be randomized in a 1:1 ratio (right/left eye), taking into account the Efron's minimization method, using the IRS.

The IRS User Guide will describe the steps of the randomization process from the subject's screening up to before IVT injection.

An algorithm with a testing hierarchy will be employed prior to randomization to determine the best- and worst-seeing eye of each subject, as follows:

1. ETDRS visual acuity score for subjects able to read the ETDRS chart. The eye with the higher ETDRS score is the best-seeing eye. For subjects who cannot read the ETDRS chart ("off chart" subjects) a standard study procedure will be used to determine visual acuity based

on counting fingers at a given distance. The eye with the best visual acuity based on this method is the best-seeing eye. If one eye of a subject is able to read letters on the ETDRS chart and one eye cannot, the eye able to read the ETDRS chart is the best-seeing eye.

2. SD-OCT parameters (to be used if there is no inter-eye difference based on Criterion 1):

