## **6. ANALYSIS SETS**

### **6.1 INTENTION-TO-TREAT**

The intent-to-treat population will consist of all subjects who are randomized and receive the actual study treatment (GS010). This population will be the population for the primary efficacy analysis.

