### Sensitivity Analyses

The primary analysis with the same model will be repeated for the following lists.

- 1) Per protocol
- 2) Randomized subjects even if they were not treated and assigned treatment by randomization instead of actual treatment received
- 3) Secondary handling of missing data
- 4) Model with geographical area effect
- 5) Model excluding major outliers if any
- 6) Analysis of absolute Week 48 LogMAR values
- 7) Baseline GCL thickness/volume and topographical map
- 8) Best or worst-seeing eye (eye status) added as a binary covariate
- 9) Duration of vision loss at the time of treatment added as a covariate in the model

All these analyses will be presented in a forest plot displaying treatment effect, 95% confidence intervals and p-value. The analysis will also be presented in tabular format.

- 10) Non-parametric Analysis: Wilcoxon signed-rank test will be performed as a sensitivity analysis to compare between all-GS010 eyes and all-Sham eyes

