#### Sensitivity Analysis

Primary analysis with the same model will be repeated for the following lists.

- 1) Per protocol
- 2) Randomized subjects including those not treated
- 3) Secondary handing of missing data
- 4) Model with country effect
- 5) Model excluding major outliers if any (defined as a standardized endpoint greater than the absolute value of 4.0)
- 6) Analysis of absolute Week 48 LogMAR values, without covariate adjustment
- 7) Baseline GCL layer thickness/volume and topographical map
- 8) Duration of vision loss at the time of treatment as a covariate

All these analyses will be presented in a forest plot displaying treatment effect, 95% confidence intervals and p-value.

10) Non-parametric Analysis: Wilcoxon Rank-Sum test will be performed as a sensitivity analysis to compare between Best-GS010 eyes and Best-Sham eyes.

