## 9.6 SAFETY ANALYSES

All safety analysis will be conducted on the Safety population and summarized by treatment actually received.

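### Both primary analyses carry an intent-to-treat label but group eyes by treatment received, and no best-eye (FDA) analysis is explicitly as-randomised

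*SAP*

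**What the plan says.** SAP section 9.5 sets one rule for all efficacy work: "All efficacy analysis will be conducted on the ITT population and analyzed by actual treatment received". Section 9.6 sets the same grouping rule for safety: "All safety analysis will be conducted on the Safety population and summarized by treatment actually received".

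In SAP section 9.5.1 the EMA primary analysis compares all GS010 eyes with all sham eyes within subjects. The FDA primary analysis compares best-seeing GS010 eyes with best-seeing sham eyes between subjects. Each is set on the ITT population and neither changes the grouping rule.

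The two sensitivity lists differ at item 2:

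- EMA: "Randomized subjects even if they were not treated and assigned treatment by randomization instead of actual treatment received"
- FDA: "Randomized subjects including those not treated"

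The protocol's ITT definition (section 12.3.1) covers "all subjects, who are randomized and receive study treatment (GS010 or sham treatment"). It defines a population and gives no grouping rule. Protocol section 12.4.1 gives none either; it speaks only of the treated eye and the sham eye. The as-treated rule therefore first appears in the SAP.

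**The concern.** Randomisation protects the comparison of eyes as they were allocated. The plan puts that comparison in a sensitivity list for EMA, leaves it unstated for FDA, and makes the as-treated comparison confirmatory. That reverses the usual order. The wording of EMA item 2 shows that the authors regarded the two groupings as different.

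If a subject is injected in the wrong eye, both eye labels are reversed relative to randomisation in the EMA analysis. In the FDA analysis that subject's best-seeing eye moves to the other arm. The FDA analysis is the more exposed, because the minimisation was designed "to balance as much as possible the two treatment groups (GS010 and sham) in the best-seeing eyes" and as-treated grouping can undo part of that balance.

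With a planned 36 subjects, one reassigned subject can shift a primary estimate visibly. If the error were in some way related to prognosis, the as-treated estimate would no longer have the protection of randomisation.

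**Working it through.** **Inputs from the SAP (section 3.3).** Effect 0.3 LogMAR, SD of the between-eye difference 0.594, 36 subjects. Alpha is 0.05, two-sided because the alternative in section 9.5.1 is two-sided. Effects below are signed so that positive favours GS010.

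**Assumptions, not in the documents.** One subject has the two eyes swapped, unrelated to outcome. The FDA analysis has 18 best-seeing eyes per arm. The SD of change is the same in both eyes, and the between-eye correlation ρ is 0 or 0.5. The calculations do not adjust for baseline, whereas the planned models do, so the figures are approximate.

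**1. The plan's own figure.** The SAP says "the SD of the difference of 0.594 would provide a power/probability of 84% to detect such a difference". The standardised effect is 0.3/0.594 = 0.505 and the noncentrality is 0.505 × √36 = 3.03. The paired t-test with 35 df then has power 83.8%. The stated 84% is reproduced.

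**2. EMA analysis, one swap.**

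- As-randomised expectation: 0.3 × (1 − 2/36) = 0.283. As-treated expectation: 0.300.
- The two estimates differ by 2d/36, where d is the swapped subject's GS010-minus-sham difference. With d of mean 0.3 and SD 0.594, the mean is 0.017 and the SD is 2 × 0.594/36 = 0.033. The 95% range is 0.017 ± 1.96 × 0.033, or −0.048 to 0.081.
- Standard error: 0.594/√36 = 0.099.
- As-randomised power: 78.6% by simulation (400,000 runs), 78.4% by a noncentral-t approximation. With two swaps the expectation is 0.267 and simulated power is 72.6%.
- Under the null, one swap unrelated to outcome leaves the rejection rate at 5.0%.

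**3. FDA analysis, one swap.**

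- Per-eye SD: 0.594/√(2(1 − ρ)), which is 0.420 at ρ = 0 and 0.594 at ρ = 0.5.
- Standard error, 18 per arm: SD × √(2/18), which is 0.140 and 0.198.
- As-randomised expectation: 0.3 × 17/18 = 0.283. As-treated grouping gives 17 against 19 eyes and expectation 0.300.
- Suppose the swapped subject was allocated GS010 in the best eye, and let y be that eye's change. As-treated minus as-randomised is (mean of the other 17 − y)/18 + (mean of the 18 sham − y)/19. Its mean is 0.3/18 = 0.017. Its SD is the per-eye SD × √[(1/18 + 1/19)² + 1/(18² × 17) + 1/(19² × 18)] = per-eye SD × 0.110, which is 0.046 at ρ = 0 and 0.065 at ρ = 0.5.

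| Analysis | As treated | As randomised | 95% range of the difference | Standard error | Power, as treated | Power, as randomised |
|---|---|---|---|---|---|---|
| EMA, paired | 0.300 | 0.283 | −0.05 to 0.08 | 0.099 | 83.8% | 78.6% |
| FDA, ρ = 0 | 0.300 | 0.283 | −0.07 to 0.11 | 0.140 | 54.7% | 49.8% |
| FDA, ρ = 0.5 | 0.300 | 0.283 | −0.11 to 0.14 | 0.198 | 31.2% | 28.2% |

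With no swap, FDA power is 54.9% (ρ = 0) or 31.3% (ρ = 0.5).

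**4. Relative size.** The expected shift of 0.017 is 0.017/0.099 = 17% of the EMA standard error and about 8% to 12% of the FDA one. At the upper end of the 95% range it is about 0.7 to 0.8 of a standard error (0.081/0.099 for EMA; 0.107/0.140 and 0.144/0.198 for FDA).

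**The case against.** The strongest reply is that nothing in the documents suggests the two rules will diverge. Every subject gets GS010 in one eye and sham in the other, and SAP section 9.4.1 describes the injection as given in the randomised eye. No swap rate is given, so every figure above depends on an assumed error. Even then the expected shift is small, and the wider ranges describe one subject's variability rather than bias. Type I error is not inflated when swaps are unrelated to outcome. All of this stands, and it limits how serious the point is.

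A second reply is that cover already exists. EMA item 2 is a full as-randomised repeat, and it also serves the all-eyes comparison that is secondary for FDA. The per-protocol analysis, item 1 in both lists, could remove a mis-injected subject. FDA item 2 may have been meant as the short form of EMA item 2, since an untreated subject can only be grouped by randomisation. This stands in part. Per-protocol removal depends on the error being classed as a major deviation, and exclusion is not as-randomised analysis. FDA item 2 does not say how treated subjects are grouped, so section 9.5 still governs them.

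A third reply is that the SAP fills a gap in the protocol and does not contradict it. That is correct. The objection here is to the rule chosen, not to a departure from the protocol.

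**Conclusion.** The concern holds. Both primary analyses are as-treated under an ITT label, only the EMA list has an explicit as-randomised repeat, and no best-eye analysis is explicitly as-randomised. This rests on the text and on no numerical assumption.

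The practical effect is zero if no eye is mis-treated. One swap moves either primary estimate by 0.017 LogMAR in expectation and, in an unfavourable case, by most of a standard error, under the assumptions listed. This is a worthwhile correction and not a fatal flaw: a pivotal result should not depend on treatment errors being unrelated to outcome when a change of wording removes that dependence.

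**What to change.** - In SAP section 9.5, state that both primary analyses group each eye by its randomised treatment.
- Add analysis by treatment actually received as a sensitivity analysis in both lists.
- Carry the as-randomised clause of EMA item 2 into FDA item 2.
- Leave section 9.6 as it is; treatment received is the right grouping for safety.

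The change must be made before the randomisation code is broken, because protocol Appendix V bars SAP amendments after that and treats additions as ad hoc.

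The cost is wording only. Results for treated subjects are identical if no eye is swapped. If one is, the primary estimate is slightly diluted: EMA power falls from about 84% to about 79%, and FDA power from about 55% to 50% (ρ = 0) or 31% to 28% (ρ = 0.5). That is the accepted price of an ITT analysis.

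This edit does not settle a separate matter. SAP section 6.1 admits to the ITT set only randomised subjects who received GS010, so untreated randomised subjects would still be outside both primary analyses.

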### **9.5.1 Primary Variable**

Primary variable will be analyzed by using two approaches:

For EMA, the change of LogMAR from baseline to Week 48 will be analyzed between all-GS010 treated eyes and all-Sham treated eyes.

The FDA has recommended comparing GS010 vs Sham in the Best-seeing eyes as a primary analysis. Therefore, for the FDA change of LogMAR from baseline to Week 48 will be analyzed between Best-GS010 treated eyes and Best-Sham treated eyes as the primary analysis.

The approach to analyze the primary variable is different for EMA and FDA. For EMA the analysis is based on intra-subject comparison of change of LogMAR from baseline to Week 48. For FDA, the analysis is based on inter-subject comparison of change of LogMAR from baseline.

The two approaches are stated below in detail:

#### Primary Analysis for EMA

The null and alternative hypotheses for the primary endpoint are defined below

$$H_0: \mu_{\text{All-GS010}} = \mu_{\text{All-Sham}}$$

$$H_1: \mu_{\text{All-GS010}} \neq \mu_{\text{All-Sham}}$$

Where  $\mu$  presents the mean change from baseline to Week 48 in LogMAR. “All” represents all eyes treated with GS010 or Sham

The primary analysis will be performed on the ITT population. The change from baseline to Week 48 in the LogMAR acuity will be the primary response. The change from baseline of all-GS010 eyes will be compared to the change from baseline of all-Sham eyes (intra-subject comparison) using a mixed model of analysis of covariance (ANCOVA) using the following terms (or covariate) in the model:

- Subject as random factor
- Eyes of the subject as random factor,
- Treatment and the
- Baseline LogMAR for each eye.

The analysis will be performed based on alpha of 0.05. The statistical significance in favor of GS010 against sham will provide evidence of the advantage of using GS010 for halting visual acuity loss or improving visual acuity in subjects with LHON with duration of vision loss of more than 6 months and up to 12 months. The difference in the mean change from baseline (adjusted mean difference) to Week 48 between the two treatment groups and associated 95% confidence interval will be reported.

The center will not be included in the analysis as the number of subjects recruited per site will be very small. However, stratification by geographical area will be performed as a sensitivity analysis. Neighboring countries can be pooled together to reach at least 9 subjects per geographical entity. The pooling will be performed during the masked review of data.

An additional model will add the treatment by geographical interaction for lack of generalizability of treatment effect purposes.

All the model diagnostics will be checked.

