### 4.3 PREDETERMINED COVARIATES AND PROGNOSTIC FACTORS

RGC layer, INL, ONL thickness/volume and topographical maps of these anatomical regions, best or worst-seeing eye (eye status) as determined prior to randomization and duration of vision loss at the time of treatment could be significant prognostic factors for the treatment effect. Sensitivity analysis will be performed for RGC layer thickness/volume and topographical map and eye status (best or worst-seeing eye) and duration of vision loss at the time of treatment by including them in the primary model as a covariate.

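### The EMA primary model leaves out eye status, which the randomisation balances, and so may give up some power if best- and worst-seeing eyes differ in untreated change beyond what baseline LogMAR explains

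*SAP*

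**What the plan says.** SAP 9.5.1 (Primary Analysis for EMA) fits the Week 48 change in LogMAR "using a mixed model of analysis of covariance (ANCOVA) using the following terms (or covariate) in the model". The terms are subject as a random factor, "Eyes of the subject as random factor", treatment, and "Baseline LogMAR for each eye". The test is two-sided: "The analysis will be performed based on alpha of 0.05". The protocol's primary model (12.4.1) has subject, treatment and baseline, also without eye status.

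The randomisation does use eye status. Under SAP 3.4, Efron's method "will be used in the randomization process to balance as much as possible the two treatment groups (GS010 and sham) in the best-seeing eyes". SAP 3.1 calls eye status a possible confounder. SAP 4.3 lists it among factors that "could be significant prognostic factors for the treatment effect".

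In the analysis plan, eye status appears in four other places:
- EMA sensitivity analysis 8: "Best or worst-seeing eye (eye status) added as a binary covariate".
- The separate best-eye and worst-eye comparisons in SAP 9.5.1.
- The time-course model in SAP 9.5.5, as a main effect and in interaction with treatment.
- The protocol's interaction check in 12.4.1.

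Neither document explains why it is left out of the EMA primary model.

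**The concern.** Balancing treatment over a prognostic factor takes most of that factor's contribution out of the true error of the treatment estimate. A model without the factor still puts that contribution in the residual. The reported standard error then exceeds the real variability, the confidence interval is wider than it need be, and the test rejects less often than its nominal level.

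In a 36-subject pivotal trial a few points of power are worth having, and the variable is already collected. Sensitivity analysis 8 cannot recover them. SAP 9.5.3 spends all of alpha on the primary analysis and treats the rest as supportive, and Protocol Appendix V rules out SAP amendments once the code is broken.

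**Working it through.** **Inputs.** From SAP 3.3: 36 subjects, SD of the between-eye difference in change 0.594, effect 0.3 LogMAR, stated power 84%; also a standardised difference of 0.50 for 85% power. From SAP 9.5.1: two-sided alpha 0.05. Assumed: g from 0 to 0.3 LogMAR, and a biased coin of 2/3 for Efron's method (the documents state neither).

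**1. The plan's own figures.**
- n = (1.960 + 1.036)² / 0.50² = 35.9, so 36, by the normal approximation. A paired t-test gives 83.1% at 36 and needs 38 for 85%.
- Second calculation: SE = 0.594/√36 = 0.099 and 0.3/0.099 = 3.03. Power is 85.8% (normal) or 83.8% (t), which matches the stated 84%.

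**2. Mechanism.** Write subject i's treated-minus-sham difference in change as τ + g·sᵢ + eᵢ, where sᵢ = +1 if the best-seeing eye is treated and −1 otherwise. With sᵢ nearly balanced, g·sᵢ averages out of the estimate. A model without eye status nevertheless sees residual variance 0.594² + g². Its standard error is inflated by √(1 + g²/0.594²):
- g = 0.1: √(1 + 0.010/0.353) = 1.014
- g = 0.2: √(1 + 0.040/0.353) = 1.055
- g = 0.3: √(1 + 0.090/0.353) = 1.120

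The random eye term does not help. With one Week 48 value per eye it cannot be separated from the residual.

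**3. Power for 0.3 LogMAR if 0.594 is the SD after removing eye status.** The closed form uses a t-test without the baseline covariate. It overstates the loss in a balanced trial, because it lets the estimate vary as much as the model reports. The simulations fit the SAP model by REML, with baseline LogMAR, with and without eye status.

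| g | Closed form, without / with | Simulated, without / with |
|---|---|---|
| 0 | 83.8% / 83.7% | 82–84% / 82–84% |
| 0.1 | 82.8% / 83.7% | about 84% / 84% |
| 0.2 | 79.7% / 83.7% | 81–83% / 83–84.5% |
| 0.3 | 74.9% / 83.7% | 76.5–81% / 84–85% |

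Two settings bracket the g = 0.3 row. With a very wide inter-eye baseline gap, baseline LogMAR absorbs more and the loss is just under 3 points (81.4% against 84.2%). When unequal baseline slopes are also allowed (within subjects −0.5, between subjects −0.1), power without the term reached as low as 77% at g = 0.2 and 74% at g = 0.3, against 82–85% with it. There the single pooled slope leaves part of the baseline gap unabsorbed, so the effective g is larger than its nominal value.

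At g = 0.3 without the term, the reported SE was 0.103–0.110 against a true SD of 0.099–0.104 in the common-slope settings. Type I error was 2.3–4.6% over all settings. With the term it scattered around 5% (4.2–6.1%).

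**4. Power if 0.594 already contains g.** The SD after adjustment is √(0.594² − g²), that is 0.586, 0.559 and 0.513 at g = 0.1, 0.2 and 0.3. Simulating the paired difference without baseline:
- g = 0.1: 84.0% without the term, 84.6% with it.
- g = 0.2: 85.1% and 87.9%.
- g = 0.3: 86.7% and 92.5%.

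**5. When baseline LogMAR does the work.** With g = 0 and a linear baseline slope of −0.6, power is 84.0% without eye status and 83.7% with it: no loss, and no material cost.

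**The case against.** The strongest reply is that eye status is mostly a ranking of baseline acuity, which is already in the model. Acuity is the first criterion in SAP 3.4, and a difference that acts linearly through baseline costs nothing (step 5). This stands as a condition on the point. It does not remove it: acuity ties are broken by ganglion-cell volume, contrast sensitivity and then investigator assessment, and SAP 5.4 derives LogMAR differently for on-chart and off-chart eyes, so a linear baseline term need not capture all of eye status.

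A reader might infer that the omission takes power below the 84% in SAP 3.3. The documents do not support that. The 0.594 is given simply as the SD of the between-eye difference in change, with no mention of adjustment for eye status. If it already contains g, the 84% is met without the term (step 4).

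A reader might also infer a biased estimate or a false-positive risk. Neither follows: near balance the error is conservative, so a positive result stays valid. Nor is balance guaranteed; the SAP seeks it only as far as possible.

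It is also fair to say that the plan does not ignore eye status, and that its stated interest is largely whether the treatment effect differs between best and worst eyes. A main effect does not answer that question, and the planned interaction and separate-eye analyses remain necessary. The remaining issue is only where the main effect sits. Finally, g = 0.3 equals the whole treatment effect the trial is planned to detect, so it is the far end of the range.

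**Conclusion.** The point holds as a conditional loss of efficiency. The EMA primary model omits a factor that the randomisation balances and that the SAP itself regards as possibly prognostic. If best- and worst-seeing eyes differ in untreated change beyond the linear baseline effect, the standard error is overstated and power is forgone: none at g = 0, about 1 point or less at 0.1, about 1 to 3 points at 0.2, and about 4 to 9 points at 0.3, with the wider settings noted in the working. These sizes rest on an assumed g and an assumed coin of 2/3. A shortfall against the stated 84% is not established. What is established is that adding the term costs essentially nothing when eye status is not prognostic and recovers power when it is.

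**What to change.** Before unmasking:
- In SAP 9.5.1 (Primary Analysis for EMA), add eye status (best or worst), as determined before randomisation, as a fixed effect beside treatment and baseline LogMAR.
- Make the present model, without eye status, sensitivity analysis 8.
- Carry the change to the Week 96 all-eyes LogMAR analysis in SAP 9.5.5, which takes over this model.
- Record the change against the primary model in Protocol 12.4.1, so that the two documents agree.

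The cost is one within-subject degree of freedom and a short edit to the SAP with a note against the protocol. No new data are needed.
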